Young MSM on PrEP face traditional and stigma-related adherence barriers, which have slowed PrEP scale-up for YMSM and may limit the public health impact. Data from 2 PrEP trials with YMSM by Hosek and colleagues^{16, 17} inform this study. In ATN 110,¹⁷ 200 18-22 year olds were provided PrEP and followed for 48 weeks, with monthly visits through week 12, followed by quarterly visits thereafter. Protective drug levels (≥ 4 doses per week) decreased from 56% at week 4 to 34% at week 48, with a noticeable drop-off when quarterly visits were implemented. The ATN 113¹⁶ trial showed that among 76 15-17 year olds, protective adherence decreased from 60% at week 4 to only 28% by week 48. Similar to ATN 110, the drop in protective TFV levels was apparent after youth transitioned from monthly to quarterly visits. Youth in both studies reported typical adherence barriers (e.g., pill size, too busy, forgetting, change in routine). Additionally, they reported PrEP-related stigma concerns, such as worrying that others will think they are HIV+ or find out that they are having sex with men. This study protocol will evaluate the PrEP-iT mobile intervention as a youth-specific strategy to improve PrEP adherence and retention in PrEP care.

Summary of the scientific premise:

- YMSM are at the highest risk for HIV acquisition in the US, and are the focus of this study.
- PrEP is a highly effective prevention strategy, but requires adherence and retention to care.
- YMSM require frequent, developmentally-appropriate supports that address traditional and stigma-related barriers to achieve full PrEP adherence and retention in care

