Tenofovir (TFV) is a primary component of the PrEP medication, and TFV drug levels will be assessed in a random subset of participants (≥50%) to evaluate objective adherence. TFV is phosphorylated in cells to TFV-diphosphate (TFV-DP), which is both pharmacologically active (in relevant cells) and demonstrates a longer intracellular half-life compared with the parent drug in plasma. The presence of TFV-DP in red blood cells (RBCs) can be measured within a dried blood spot (DBS) analysis. TFV-DP levels in DBS will be measured by [name] Laboratory using established standardized protocols.²¹ Through this methodology, estimates can be made of the number of TDF doses taken over a 7-day period.

Blood collection for DBS sample acquisition can be done via venipuncture or fingerstick. Blood drawn by venipuncture should utilize an EDTA collection tube, and processed within 60 minutes of collection by applying the blood directly onto the designated circle on the collection card. Blood from finger stick should be spotted on the card immediately by touching the blood drop to the card without pressing the finger to the card. After blood is applied, the cards are air dried for several hours (overnight is acceptable) and then stored in low gas-permeability bags. DBS card specimens are then stored under frozen conditions (20°C, or -80°C) until analysis. Specimens will be labeled with PID, study, date, and visit type, but will not include any individual identifying information. Please see the study MOP for additional step by step details on blood collection, processing to DBS cards, storage and shipping instructions.

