5. STATISTICAL METHODS

5.1. Sample Size Considerations

The sample size for this proof-of-concept study (n=40 per group; n=80 total) is consistent with recommendations of sample sizes for pilot studies of this nature.²² Power calculations are presented for the two adherence outcomes: TFV-DP levels and the adherence score. For the TFV-DP levels (n=20 in each arm), prior research suggests that approximately 40% will have levels TFV-DP levels >700 fmol/punch at 3 months. Assuming a type I error of 5% and using a chi-square test statistic, we have 80% power to detect a relative risk of 2.0 or larger (i.e., that the intervention group is 2.0 times as likely to have high levels of TFV-DP as the control group). Adherence may decrease by 6 months, increasing our detectable effect. If we assume 30% adherence at 6 months, we have 80% power to detect a relative risk of 2.4 or higher. For the adherence score derived from Wilson et al.'s²³ 3-item measure, prior research on ART therapy suggests a standard deviation of approximately 20.²³ Assuming we will see the same standard deviation among PrEP users and a type-1 error rate of 5%, we have 80% power to detect a difference in adherence scores of 12.7 units between the two groups. This is approximately half of a standard deviation change, and should provide good preliminary evidence to inform future trials.

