5.2. Randomization Procedures

Participants will be randomized in a 1:1 allocation to either: a) the mobile intervention of PrEP iT! in addition to usual care, or b) a control condition that consists only of usual care. The randomization sequence will be stratified by age (18-24 v. 25-29 yrs) and use blocks of four. Given the nature of the intervention, treatment allocation will not be blinded following randomization.

All study staff and participants will be unaware of randomized group allocation until enrollment and randomization procedures are completed. Following screening and enrollment, participant eligibility will be re-confirmed. After completion of the randomization CRF, the treatment allocation will be revealed within the study database. Research staff will

then instruct participants on their study group, and participants within the mobile intervention arm will be guide through setup of the PrEP iT! web application.

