5.3. Analysis Plan

Feasibility of delivering the intervention will be assessed by examining the percentage of eligible people who are successfully recruited into the study and by the percentage of participants retained at each visit. Chi-square tests (or Fisher's exact test, for small cell counts) will be used to compare the intervention and control groups in the proportions of participants retained at both 3- and 6-month follow-up. We will use the following retention cut-off percentages to assess feasibility: a) 90+ = strong feasibility; b) 80-89% = acceptable feasibility; c) 70-79% = modest feasibility with a need for improvement; d) <70% = unacceptable feasibility.

Acceptability will be measured using a 10-item self-report System Usability Scale (SUS)²⁴ computed in the intervention arm over time (at 3- & 6-months). The average SUS score across 400 studies was 68²⁴ (possible range 0-100); therefore, an average score of ≥ 68 will be considered acceptable and ≥ 80 highly acceptable. We will estimate overall acceptability and changes over time. Acceptability will further be assessed by recording the frequency of *PrEP iT!* interaction (average number of uses per week) over follow-up time.

The preliminary impact of the mobile intervention will specifically be evaluated. We will focus on two adherence measures to estimate the preliminary efficacy of the *PrEP iT!* intervention. Objective adherence will be assessed via TFV-DP levels in DBS samples ($n \geq 20$ per treatment arm). TFV-DP data will be dichotomized into high levels (≥ 700 fmol/punch) vs low levels (< 700 fmol/punch) and the difference in proportion of high levels of TFV-DP between treatment arm will be estimated using chi-square or Fisher's exact test at both 3 and 6 months. In a separate analysis, we will keep TFV-DP as a continuous variable and examine differences between control and intervention groups using T-tests and permutation tests. Second, at 3 and 6 months, we will use the validated 3-item self-report adherence measure developed by Wilson and his colleagues.²³ T-tests will compare the mean adherence score between intervention and control arm at 3 and 6 months. Permutation tests will also be used to test for treatment group differences, since they do not require distributional assumptions and are typically more robust.

6. REFERENCES:

1. Centers for Disease Control and Prevention. HIV Surveillance Report, 2016. 2017.

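### Randomization is stratified by age, but the planned t-tests for the 3-item adherence score and continuous TFV-DP do not use the stratum, and the permutation scheme is not stated

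*Combined protocol and SAP*

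**What the plan says.** Section 5.2 sets out the allocation: "The randomization sequence will be stratified by age (18-24 v. 25-29 yrs) and use blocks of four". Age is the only stratification factor.

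Section 5.3 gives the analyses of the two continuous adherence outcomes. For the self-report score, "T-tests will compare the mean adherence score between intervention and control arm at 3 and 6 months". For TFV-DP kept continuous, the plan will "examine differences between control and intervention groups using T-tests and permutation tests". On the permutation tests it adds: "Permutation tests will also be used to test for treatment group differences, since they do not require distributional assumptions and are typically more robust". No test in 5.3 has a stratum term or covariate. Whether permutations respect the age strata is not stated.

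Section 5.1 sizes the score comparison at 40 per arm with SD 20: "we have 80% power to detect a difference in adherence scores of 12.7 units between the two groups". Section 3.5 limits the TFV-DP assays: "TFV drug levels will be assessed in a random subset of participants" (at least half, and 20 per arm in the power calculation). It does not say that the subset is balanced by age.

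**The concern.** Stratified blocks make the two arms nearly identical in age mix. If age predicts adherence, that part of the outcome variance no longer contributes to the difference between arms. A two-sample t-test still counts it as noise, as does a permutation test that shuffles labels across all participants. The reported standard error is then larger than the true one.

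What is at stake is the interval around a secondary, preliminary effect estimate. That still has some importance, because sections 2.1 and 5.1 give informing a later trial as the purpose of the pilot. Separately, a permutation test is defined by its reassignment scheme. Leaving the scheme unstated leaves the analyst a choice.

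**Working it through.** **1. Reproduce the plan's figure.** Inputs from 5.1: 40 per arm, SD 20, type I error 5%, power 80%. The plan does not state sidedness.
- Normal approximation: (1.960 + 0.842) × 20 × √(2/40) = 12.53 units.
- Noncentral t, two-sided: 12.69 units, which matches the stated 12.7. One-sided would give 11.2.

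So 12.7 is an unadjusted two-sided t-test calculation that uses the total SD.

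**2. What stratification does to the t-test.** Let d be the age difference in total SDs, with a 50/50 age split (assumed). Age then explains R² = d²/4 of the variance. With the arms balanced on age:
- true SE ≈ SD × √(1−R²) × √(2/n), with n per arm
- SE reported by the t-test ≈ SD × √(2/n)
- actual type I error ≈ 2 × [1 − Φ(1.96/√(1−R²))]
- detectable difference with adjustment = 12.69 × √(1−R²)

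**3. Which d?** The documents give none for 18-24 v. 25-29. The nearest figures are two separate youth cohorts in section 1.1. At ages 18-22, protective drug levels "decreased from 56% at week 4 to 34% at week 48"; at ages 15-17, "protective adherence decreased from 60% at week 4 to only 28% by week 48". On a probit scale:
- Week 4: Φ⁻¹(0.60) − Φ⁻¹(0.56) = 0.253 − 0.151 = 0.10 SD, favouring the younger cohort.
- Week 48: Φ⁻¹(0.34) − Φ⁻¹(0.28) = −0.412 + 0.583 = 0.17 SD, favouring the older cohort.

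These are not the trial's strata, so they are indicative at most. The range used is 0.17, 0.3, 0.5 and 0.8 SD.

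**4. Score, N=80.** Simulation of blocks of four within age: normal outcomes, total SD 20, true effect 0 or 12.69 units, 40,000 trials per scenario. Monte Carlo SE is about 0.1 point for type I error and 0.2 for power. The adjusted model contains arm and age stratum, and its type I error was 4.9-5.0%.

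| Age difference (SD) | R² | Type I error by formula | Type I error, t-test simulated | Power, t-test | Power, adjusted | CI narrower by | Detectable difference, adjusted |
|---|---|---|---|---|---|---|---|
| 0.17 | 0.007 | 4.9% | 4.9% | 79.9% | 80.2% | 0.4% | 12.64 |
| 0.3 | 0.0225 | 4.7% | 4.7% | 80.4% | 80.9% | 1.1% | 12.54 |
| 0.5 | 0.0625 | 4.3% | 4.2% | 80.6% | 82.4% | 3.2% | 12.29 |
| 0.8 | 0.16 | 3.2% | 3.2% | 81.6% | 86.2% | 8.5% | 11.63 |

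With a 70/30 age split, the gains at 0.5 and 0.8 SD are 1.5 and 3.7 points. With 80% retention at 0.3, 0.5 and 0.8 SD, power is 70.6%, 70.9% and 71.6% by t-test against 71.3%, 73.1% and 77.7% adjusted.

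**5. Reported SE against true variability.** At R² = 0.10 and N=80, both the unadjusted and adjusted estimates have a true SD of 4.28 units. The t-test reports a mean SE of 4.46 and the adjusted model 4.23. The loss is therefore an overstated SE, not a noisier estimate.

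**6. TFV-DP, random 20 per arm, true effect 0.909 SD** (the detectable effect at that size).
- Power at 0.17, 0.3, 0.5 and 0.8 SD: 79.8%, 79.8%, 80.2%, 80.0% by t-test against 79.4%, 80.1%, 81.8%, 85.1% adjusted. Break-even lies between 0.17 and 0.3 SD.
- Random sampling partly undoes the age balance, so the t-test is less conservative: type I error at 0.8 SD is 4.2%, against 3.2% in the full sample.
- The power gain is similar to that for the score: 1.6 and 5.1 points at 0.5 and 0.8 SD, against 1.8 and 4.6. Here the unadjusted estimate is itself slightly more variable (6.19 v. 6.05 at R² = 0.10, on the SD-20 scale).

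**7. Permutation tests, N=80** (20,000 trials, 499 permutations), at 0.17, 0.3, 0.5 and 0.8 SD.
- Free reassignment: type I error 4.9%, 4.8%, 4.1%, 3.2%; power 79.6%, 80.4%, 80.6%, 81.8%.
- Within age strata: type I error 4.7-5.0%; power 79.7%, 81.1%, 82.3%, 86.1%.

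**8. If age has no effect.** Power unadjusted against adjusted: N=80, 80.2% v. 80.3%; 20 per arm, 79.9% v. 79.3% with a CI 0.7% wider. Permutation, free against within age: 79.9% v. 79.7%.

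**The case against.** The strongest reply is that nothing in the documents shows a loss. The only anchor, 0.17 SD or less with inconsistent sign, gives 79.9% v. 80.2% for the score and is slightly unfavourable to adjustment for TFV-DP. The larger scenarios are pure assumption. At SD 20, 0.5 SD is 10 units and 0.8 SD is 16 units between adjacent age bands, and 16 exceeds the 12.7-unit treatment difference the score comparison is sized for. The outcomes are secondary in a pilot, 5.1 is consistent with the unadjusted test, and the simulations assume normality. All of this stands, and it is why the point is optional. It does not remove the case for a change that costs almost nothing.

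A reader might infer four stronger things that the documents do not support:
- **That ignoring the stratum invalidates the tests.** It does not. The error is conservative and type I error is not inflated.
- **That the permutation tests ignore age.** Section 5.3 is silent, and permuting within strata is compatible with it. The point is certain only for the t-tests.
- **That the unadjusted score estimate is itself less precise.** At N=80 its true variability is essentially the same; only the reported SE and interval are too wide.
- **That TFV-DP is less affected throughout.** The conservatism is weaker there, but the power gain is similar.

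**Conclusion.** The point holds as a minor efficiency and specification matter. The t-tests are valid but do not use the age stratum, and the permutation scheme needs stating. If age predicts adherence, the t-test at N=80 overstates the standard error. The gain from adjustment is immaterial at 0.3 SD or less, about 2 power points at 0.5 SD and 4 to 5 at 0.8 SD (3.7 with a 70/30 age split, 6.1 with 80% retention). These sizes rest on assumed age differences, normal outcomes, a total SD of 20 and, except where noted, equal age strata. The primary feasibility and acceptability conclusions do not depend on it. Severity: could be changed.

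**What to change.** In section 5.3:
- Analyse the 3-item score and continuous TFV-DP at 3 and 6 months with a linear model containing arm and the age stratum used at randomization. Report the adjusted difference with its 95% CI.
- Keep the t-tests as supportive.
- State that the permutation tests reassign arm within age strata.
- Leave the chi-square or Fisher analysis of dichotomized TFV-DP as planned.
- Do not extend the adjustment to how participants qualified under inclusion criterion 7. No figure supports it, and it would need a new classification rule.

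The cost is SAP wording and one model degree of freedom, with no new data, visits or assays. If age does not matter, simulated power changes by under 0.2 points for the N=80 model and falls by about 0.2 points for permutation within age strata. For TFV-DP at 20 per arm it falls by about 0.6 points.

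### The self-reported adherence score is t-tested separately at 3 and 6 months with no main comparison named, and men seen only at 3 months drop out of the 6-month test

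*Combined protocol and SAP*

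**What the plan says.** The combined protocol and SAP has the men assessed at 3 and 6 months (sections 2.1 and 2.7). For the three-item self-report score, section 5.3 states: "T-tests will compare the mean adherence score between intervention and control arm at 3 and 6 months". It adds: "Permutation tests will also be used to test for treatment group differences". It does not say which visit, or which of the two kinds of test, decides. For this outcome it gives no joint model over visits, no baseline term, no rule for reading two results together and no treatment of a missed visit.

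Section 5.1 sizes one comparison. The sample is "n=40 per group; n=80 total", and the variability comes from elsewhere: "prior research on ART therapy suggests a standard deviation of approximately 20". The result is that "we have 80% power to detect a difference in adherence scores of 12.7 units between the two groups". The visit is not given, although the same section gives separate 3- and 6-month figures for high TFV-DP levels.

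Self-reported adherence is a secondary outcome (section 2.6); the primary outcomes are feasibility and acceptability. Section 5.3 grades retention of 80-89% as acceptable.

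**The concern.** Each man can supply two scores, but each planned test looks at one visit and ignores the other. Two consequences follow.

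- **Interpretation.** With two unranked tests, each at the full 5%, the plan does not say what counts as a positive finding. If either one counts, the error rate for this outcome is above 5%.
- **Incomplete follow-up.** A 6-month t-test uses only men with a 6-month score. The 3-month score of a man lost later says something about where he would have been at 6 months, and the planned test does not use it.

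Section 1.2 hypothesises better adherence, section 5.3 treats the score as one of two measures of preliminary efficacy, and section 2.1 says the pilot is to inform a later trial. A result that is significant at one visit and not at the other would reach the planners of that trial with no agreed reading.

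**Working it through.** **Inputs from the documents.** 40 men per arm, 1:1 allocation, SD 20, type I error 5%, power 80%, stated detectable difference 12.7 (sections 5.1 and 5.2); 80% as the lower edge of acceptable retention (section 5.3).

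**Assumptions.** Two-sided testing, which the plan does not state but which reproduces its figure. Equal SD at both visits. A within-man correlation ρ between the 3- and 6-month scores, which the documents do not give; 0.5 to 0.7 is used as the working range and 0.3 to 0.9 as the wide range. No baseline score is used: Table 2 does not list the three-item measure by name.

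**1. The plan's own figure.** The standard error of the arm difference at one visit is 20 × √(2/40) = 4.472. With the noncentral t on 78 degrees of freedom, the detectable difference at 80% power is 12.69, and power at 12.7 is 80.1%. The stated 12.7 is reproduced, for one visit with all 80 men seen.

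**2. Chance that at least one visit is significant under no effect.** The two test statistics are treated as bivariate normal with correlation ρ, and the chance is 1 − P(|Z₁| < 1.96 and |Z₂| < 1.96).

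| ρ | At least one significant |
|---|---|
| 0.3 | 9.5% |
| 0.5 | 9.1% |
| 0.6 | 8.8% |
| 0.7 | 8.3% |
| 0.9 | 7.0% |

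The ceiling, for independent tests, is 1 − 0.95² = 9.75%.

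**3. The 6-month comparison with 80% retention.** Suppose all 40 men per arm are seen at 3 months and 32 at 6 months.

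- t-test on 32 per arm: detectable difference 14.2; power at 12.7 is 71%.
- Repeated-measures model: the per-arm variance of the 6-month mean is 20² × [(1 − ρ²)/32 + ρ²/40].
  - ρ = 0.5: 0.75/32 + 0.25/40 = 0.02969, an effective 33.7 men per arm; detectable difference 13.9.
  - ρ = 0.7: 0.51/32 + 0.49/40 = 0.02819, an effective 35.5 men per arm; detectable difference 13.5.

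The gain is 0.3 to 0.7 units. With 40 of 40 seen, the bracket becomes 1/40 whatever ρ is, so the model's 6-month contrast returns to 12.7 and matches the t-test.

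**4. If the average of the two visits were the main contrast (complete data).** The SD of a man's two-visit mean is 20 × √((1 + ρ)/2).

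| ρ | SD of mean | Detectable difference | Power, 12.7 at both visits | Power, 12.7 at one visit and 6.35 at the other |
|---|---|---|---|---|
| 0.5 | 17.32 | 11.0 | 90% | 68% |
| 0.7 | 18.44 | 11.7 | 86% | 63% |
| 0.9 | 19.49 | 12.4 | 82% | 58% |

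The last column uses an average effect of (12.7 + 6.35)/2 = 9.525.

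**5. Power if either visit counts.** With a true difference of 12.7 at both visits, the bivariate normal gives 92%, 91% and 89% at ρ = 0.5, 0.6 and 0.7.

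**The case against.** A reader might infer that separate tests both waste half the data and inflate the error. The documents do not support charging both in full, for three reasons.

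- With complete data and no baseline term, the visit-specific contrasts of a mixed model are essentially the planned t-tests. The larger gain in step 4 comes from asking a different question, about the two-visit average.
- The two harms belong to different readings of the plan. If one visit decides, there is no inflation. If either visit counts, power is about 89-92% and no lower than the 86-90% of the average over ρ 0.7 to 0.5; only the error rate suffers.
- Keeping the visits apart is a defensible choice. Section 1.1 reports protective drug levels falling over follow-up in two youth PrEP studies, and section 5.1 allows for lower adherence at 6 months. These figures concern the level of adherence, not the arm difference, but equal effects at both visits cannot be taken for granted. If the effect is halved at one visit, the average has 63-68% power at ρ 0.7 to 0.5, below the 80% of a test at the stronger visit alone.

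It is also true that a mixed model does not by itself remove the second chance. Naming one contrast does, and that could be done with t-tests. Finally, this is a secondary outcome in a pilot, and no decision rule in the plan depends on either p-value.

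All of this stands. It leaves two gaps: no main comparison is named, and 3-month scores go unused when the 6-month visit is missed.

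**Conclusion.** The point holds in a limited form. Reading significance at either visit as evidence of efficacy carries a false-positive chance of about 8-9% at correlations of 0.5 to 0.7, and 7.0-9.5% over 0.9 to 0.3. At 80% retention at 6 months, the t-test's detectable difference is 14.2 units, against about 13.9 or 13.5 from a repeated-measures model at ρ = 0.5 or 0.7. That is a real but small recovery, and it rests on an assumed correlation, complete 3-month data and scores missing at random.

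Two stronger conclusions do not follow. The 12.7 units in section 5.1 is not wrong; it is right for one visit with full follow-up. Nor is the two-visit average shown to be the better main contrast; that depends on whether the effect is similar at both visits. Priority is modest, and formal multiplicity control is not needed in a pilot.

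**What to change.** In section 5.3:

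- Analyse the score with one mixed model for repeated measures (arm, visit, arm-by-visit, unstructured covariance), including every man with at least one follow-up score.
- Name one main contrast in advance: the 3-month difference, the 6-month difference or their average, at the sponsor's choice. State in section 5.1 which one the power figure refers to. If it is the average, the figure becomes 11.0-11.7 at assumed correlations of 0.5-0.7, given complete data and equal effects at both visits.
- Report both visit-specific differences from the same model with 95% confidence intervals, whichever contrast is chosen.
- Run the permutation test on that same main contrast.
- Use the same form for continuous TFV-DP.

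The cost is SAP wording and a standard model, with no new data, visits or participants. There are two downsides to record. An average dilutes an effect that is present, or larger, at only one visit, which is why both visit estimates must stay in the report. The model also relies on a missing-at-random assumption, which the plan should state.

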2.3. Eligibility Criteria

Inclusion criteria:

- 1) Prescribed PrEP by a healthcare provider;
- 2) Self-reported 18-29 years of age;
- 3) Assigned male at birth;
- 4) Current male gender identification;
- 5) Gay, bisexual or other non-heterosexual identity or has had sex with a man in the past year;
- 6) HIV negative (HIV negative test in the past 3 months)

- 7) Either started or restarted PrEP in the past 30 days or started PrEP more than 30 days ago and self-reports not always taking PrEP in the past 30 days;
- 8) English-speaking (as the intervention will be built in English);
- 9) Able to meet with project staff at baseline and follow-up visits;
- 10) Regular access to SMS or the internet, either through a mobile device, tablet computer, and/or desktop or laptop computer.

Additional exclusion criteria:

- Not prescribed PrEP by a healthcare provider;
- HIV positive (by a reactive HIV antibody or detectable HIV RNA level);

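### The self-reported adherence score is compared without adjustment for how each man met criterion 7, a plausible predictor of the score; the test is valid and the only loss is precision, of a size the documents do not fix

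*Combined protocol and SAP*

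**What the plan says.** Section 5.3 analyses the 3-item self-report score visit by visit: "T-tests will compare the mean adherence score between intervention and control arm at 3 and 6 months". A second analysis follows: "Permutation tests will also be used to test for treatment group differences, since they do not require distributional assumptions". No covariate, stratum or baseline adherence term is named for either, and the score is specified at 3 and 6 months only.

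Section 2.3, criterion 7, offers two routes in. The first is "Either started or restarted PrEP in the past 30 days", which carries no adherence condition. The second is "started PrEP more than 30 days ago and self-reports not always taking PrEP in the past 30 days", which selects on recent imperfect adherence.

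Section 5.2 states: "The randomization sequence will be stratified by age (18-24 v. 25-29 yrs) and use blocks of four". Route of entry is not a stratification factor. The same section has eligibility re-confirmed before the allocation is revealed.

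Section 5.1 gives the score its own power statement: "we have 80% power to detect a difference in adherence scores of 12.7 units between the two groups". It rests on a single SD of about 20, borrowed from antiretroviral therapy research.

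**The concern.** The score measures adherence, and one of the two entry routes is defined by recent self-reported adherence. If the two groups still differ at 3 and 6 months, that difference sits in the error term of an unadjusted comparison and widens the interval. The arms can also differ by chance in their mix of the two groups, and nothing in the design or the analysis takes that into account for the particular trial that is run.

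This matters somewhat because the score is one of only two adherence measures used to estimate preliminary efficacy. The other, TFV-DP, is planned for about 20 men per arm. Section 2.1 says that the pilot is meant to inform a later trial, so a tighter estimate has some value. The stated 80% power at 12.7 units also leaves no slack.

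**Working it through.** **Inputs from the documents.** 40 per arm, SD 20, type I error 5%, 80% power, 12.7 units (section 5.1). Sidedness is not stated.

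**Assumptions, because the documents are silent.** p is the share entering as established users. D is the difference in mean follow-up score between the two entry groups. I show p = 0.25 (0.75 gives the same result) and p = 0.5, with D from 5 to 20 units.

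**1. The plan's own figure.** Standard error of the difference = 20 × √(2/40) = 4.47. A two-sided two-sample t-test on 78 df (noncentral t) gives 80% power at 12.69 units, and 80.1% power at 12.7. The stated figure reproduces. A one-sided test would give 11.2 units, so the plan evidently used a two-sided test.

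**2. Validity of the unadjusted test.** In 20,000 simulated trials with no treatment effect, p = 0.5 and D = 15, the t-test rejected in 5.1%. Type I error is held.

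**3. Gain from adjustment, taking SD 20 as the total SD.** The share of variance explained by entry route is R² = p(1−p)D²/20², and the residual SD is 20√(1−R²). Example: p = 0.5 and D = 10 give R² = 0.25 × 100/400 = 0.0625 and a residual SD of 19.36. The table uses 76 df (arm, entry route and age stratum fitted) and assumes that age explains nothing.

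| D (units) | p | R² | Residual SD | Detectable difference | Power at 12.7 |
|---|---|---|---|---|---|
| 5 | 0.25 | 0.012 | 19.88 | 12.6 | 80.5% |
| 5 | 0.5 | 0.016 | 19.84 | 12.6 | 80.7% |
| 10 | 0.25 | 0.047 | 19.53 | 12.4 | 81.9% |
| 10 | 0.5 | 0.063 | 19.36 | 12.3 | 82.5% |
| 15 | 0.25 | 0.105 | 18.92 | 12.0 | 84.2% |
| 15 | 0.5 | 0.141 | 18.54 | 11.8 | 85.6% |
| 20 | 0.25 | 0.188 | 18.03 | 11.4 | 87.5% |
| 20 | 0.5 | 0.250 | 17.32 | 11.0 | 89.9% |

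If neither covariate predicts the score (R² = 0), power at 12.7 is still 80.1% to one decimal.

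**4. If SD 20 holds only within an entry group.** The total SD is then √(400 + p(1−p)D²). At p = 0.5, unadjusted power at 12.7 is 79.5%, 77.7%, 74.7% and 70.8% for D = 5, 10, 15 and 20, and adjustment restores 80.1%. The documents do not say which reading of the SD applies.

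**5. Chance imbalance.** At p = 0.5, treating entry route as simply randomized, the SD of the between-arm difference in shares is √(0.25 × 2/40) = 0.112, or 11 percentage points (95% range about ±22). With D = 10, a one-SD imbalance moves the estimated treatment difference by 0.112 × 10 = 1.1 units, against a standard error of 4.47.

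**The case against.** The strongest reply is that no section shows entry route to predict the 3- or 6-month score. There are reasons to expect weak separation. One missed dose in 30 days is enough to qualify as an imperfect adherer. The recent group includes restarters, who under section 2.2 had gone at least 3 months without PrEP. Section 1.1 cites youth trials in which only 56% and 60% had protective drug levels at week 4, so new users are not uniformly adherent. All of this stands, and it is why the predictor is called plausible rather than known.

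It also stands that the stakes are modest. Feasibility and acceptability are the primary outcomes, and section 5.1 justifies the 80 men by pilot-study recommendations before presenting power. Simple t-tests with permutation tests are a conventional choice in such a study.

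Three stronger readings are tempting, and the documents support none of them:

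- A reader might infer that the comparison is biased or its error rate inflated. It is not: allocation is random, and chance imbalance in entry route is already part of the t-test's standard error.
- A reader might infer a gain of about 10 points of power, from a correlation of 0.5 between entry route and score. For a two-group covariate that needs a 20-unit gap and an even split, and neither figure is in the documents. Even a 5-point gain needs a gap of about 14 units at an even split, more than the 12.7-unit treatment effect.
- A reader might infer that the covariate is ready to use. Table 2 lists only a verification of eligibility, which could be stored as a single yes/no, and a man who restarted within 30 days may meet both routes.

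None of this is a reason against adjusting, since an uninformative covariate costs almost nothing. It does limit what may be claimed for the change.

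**Conclusion.** The point holds as a precision point only. The plan leaves unused a pre-randomization characteristic that plausibly bears on the score, and balances it neither by design nor by analysis. For gaps of 5 to 10 units the gain is about 0.4 to 2.5 points of power, which is small. It becomes material at about 15 units (roughly 4 to 6 points), and reaches about 7 to 10 points only at a full-SD gap. These figures assume that SD 20 is the total SD, that all 40 men per arm are analysed, and that between a quarter and three quarters enter by each route. The stated 12.7 units is correct on the plan's own inputs; it would be somewhat optimistic only if SD 20 describes variation within an entry group. The change is worth making because it is nearly free, not because the present analysis is wrong.

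**What to change.** In section 5.3, pre-specify for each visit a linear model of the 3-item score on arm, age stratum (18–24 v. 25–29) and an entry-route indicator. Code the indicator without overlap: any man who started or restarted within 30 days is recent, whatever his earlier use, and all others are established. Report the adjusted mean difference with its 95% confidence interval. Run the permutation test on the same adjusted statistic, permuting within the randomization strata. Keep the unadjusted t-test as a supporting result.

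Record the entry route as its own item when eligibility is verified, and report its split by arm. Do not add a baseline score for established users only: the analysis plan names no baseline score, and a term that exists for one group needs a coding rule of its own.

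The cost is a short rewording of section 5.3, one recorded item, two degrees of freedom (78 to 76) and a covariate fixed before outcome data are seen. No extra visits or participants are needed.
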